Based on the Mackie scale, Stage 1 NK is defined by the presence of an epithelial dystrophy or punctate keratopathy accompanied by corneal hypoesthesia. Stage 1 NK requires discontinuation of all topical medications and the administration of preservative-free artificial tears (PF-AT). While some Stage 1 NK patients may heal, many cases progress to Stage 2 NK. Based on the Mackie scale, Stage 2 NK is defined by the presence of a PED. The goal of Stage 2 treatment is to avoid progression of the disease to a corneal ulcer. The same therapeutic approaches as in Stage 1 are used in patients with Stage 2 often accompanied by the addition of patching or therapeutic contact lenses and the use of prophylactic antibiotics to prevent the risk of corneal infection. Based on the Mackie scale, Stage 3 NK is defined by the presence of a corneal ulcer, which may progress to corneal melting and perforation. When a corneal ulcer develops, therapy is aimed at promoting corneal healing and preventing corneal melting or perforation. Surgical procedures at this stage (tarsorrhaphy, flap procedures, and amniotic membrane transplantation) can preserve or restore ocular integrity but at the expense of cosmetic appearance and visual function. ^[2, 3] As of today, the only Food and Drug Administration (FDA) approved pharmacologic therapy for the treatment of NK is

OXERVATE™ 0.002% (20 mcg/mL) cenegeamin-bk bj ophthalmic solution, a recombinant human nerve growth factor (rhNGF).^[4, 5]

Nerve growth factor (NGF) is a polypeptide essential for the survival and growth of sympathetic and sensory neurons, and for differentiation of neurons in the central nervous system. It binds with at least two classes of receptors: high-affinity tropomyosin receptor kinase A (TrkA), a transmembrane tyrosine kinase, and Low-Affinity Nerve Growth Factor Receptor (LNGFR), also known as p75 neurotrophin receptor (p75NTR).^[6, 7]

NGF and its receptors TrkA and p75 are expressed in the anterior segment of the eye (iris, ciliary body, lens, cornea, and conjunctiva), and NGF is released in the aqueous humor. Several pieces of experimental evidence suggest that NGF affects all tissues of the anterior ocular segments, playing a crucial role in the physiopathology of several anterior ocular segment diseases.^[8, 9]

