3.2 A SUMMARY OF CLINICAL DATA

The safety, efficacy, and FDA approval of OXERVATE™ 0.002% (20 mcg/mL) cenegermin-bk bj ophthalmic solution, was based upon a total of 151 patients with NK who completed one of two, eight-week, randomized controlled multi-center, double-masked studies. In the first study conducted in Europe, CCI [REDACTED] patients were randomized into three different groups. One group received OXERVATE™ 0.002% (20 mcg/mL) cenegermin-bk bj ophthalmic solution, a second group received 10 mcg/mL cenegermin, and the third group received vehicle.^[14] In the second study conducted in the US, CCI [REDACTED] patients were randomized into two groups. One group was treated with OXERVATE™ 0.002% (20 mcg/mL) cenegermin-bk bj ophthalmic solution, and the other group was treated with vehicle.^[15] All eye drops in both studies were given six times daily at 2-hour intervals in the affected eye(s) for eight weeks. In the first study, only patients with the disease in one eye were enrolled, while in the second study, patients with the disease in both eyes were treated in both eyes (bilaterally), the worse eye was considered the study eye for efficacy evaluations. Complete corneal healing (defined as absence of staining of the corneal lesion and no persistent staining in the rest of the cornea at eight weeks) was demonstrated in 72 percent of patients treated with OXERVATE™ 0.002% (20 mcg/mL) cenegermin-bk bj ophthalmic solution compared to 33.3 percent of patients ($p<0.001$) treated with vehicle in the REPARO trial. For the US trial, CCI [REDACTED] 65.2 percent of patients treated with OXERVATE™ 0.002% (20 mcg/mL) cenegermin-bk bj ophthalmic solution compared to 16.7 percent of patients treated with vehicle had complete corneal healing at week-8.^[14, 15]

The data from these two studies were enclosed into the biologics license application (BLA), and the FDA granted the approval for OXERVATE™ 0.002% (20 mcg/mL) cenegermin-bk bj ophthalmic solution for the treatment of all stages of NK.^[4]

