10.3 STATISTICAL METHODOLOGY

Statistical analysis will be performed by the clinical research organization (CRO) appointed by Dompé.

Appropriate descriptive statistics will be produced by treatment arms according to the nature of the variable. For continuous data, number of observations, mean, standard deviation, median and range (minimum and maximum) and 95% confidence intervals will be presented. For categorical data, frequency distributions and percentages with exact 95% confidence intervals will be presented.

Unless otherwise specified, the significance level used for statistical testing (for descriptive purposes) will be 0.05 and two-sided tests will be used. All patient data collected on the CRF will be listed by patient and center.

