5 ANALYSIS OF EFFICACY

All efficacy analyses will be considered exploratory and performed based on the observed cases in the FAS population. No missing data imputation will be considered.

For continuous efficacy endpoints, descriptive statistics of the observed and change from baseline will be tabulated by visit where that endpoint is assessed. Where appropriate, the asymptotic 95% confidence intervals of mean change from baseline will be presented as well as p values from one-sample t-test and Wilcoxon signed rank test (depending on the distribution of the data) to compare the observed values vs baseline.

For responder/categorical efficacy endpoints, analyses will include percentage of responders/categorized results, and associated exact (Clopper-Pearson) 95% confidence intervals where appropriate as well as p values from a binomial test to assess that responder rates are greater than zero.

- Percentage of patients who had corneal epithelial healing at Week 8 in the DEFENDO Study, who maintain healing at Month 24 and Month 30 of the long-term follow-up

The patients who had corneal epithelial healing at Week 8 and maintain healing at Month 24 and Month 30 will be summarized as a binary goal attainment variable (Yes/No) based on the subset of patients who achieved corneal epithelial healing at Week 8, as determined by the CRC.

- Percentage of patients who did not have corneal epithelial healing at Week 8 in the DEFENDO Study who have a healed corneal epithelium at Month 24 and Month 30 of the long-term follow-up

The patients who did not have corneal epithelial healing at Week 8 and who have corneal epithelial healing at Month 24 and Month 30 will be summarized as a binary goal attainment variable (Yes/No) based on the subset of patients who did not have corneal epithelial healing at Week 8, as determined by the CRC.

- Percentage of patients who achieved an improvement in corneal sensitivity at Week 8 in the DEFENDO Study who still have improvement in corneal sensitivity at Month 24 and Month 30 of the long-term follow-up

The improvement in corneal sensitivity is defined as change from baseline > 0 (cm) of the study eye. The patients who achieved an improvement in corneal sensitivity at Week 8 and still have improvement in corneal sensitivity at Month 24 and Month 30 will be summarized as a binary goal attainment variable (Yes/No) based on the subset of patients who achieved an improvement in corneal sensitivity at Week 8.

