7 DETERMINATION OF SAMPLE SIZE

The sample size for this study is not based on hypothesis-testing and power considerations but is determined by the number of patients from the DEFENDO Study who will rollover to the DEFENDO Long-Term Follow-up Study. The DEFENDO Study enrolled a total of 37 patients.

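### SAP 5 tests responder rates against zero, a null that in exact form any single responder rejects, so the p-value says nothing about a lasting treatment effect

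*SAP*

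**What the plan says.** SAP 5 sets the rule for this class of endpoint: "For responder/categorical efficacy endpoints, analyses will include percentage of responders/categorized results", with exact intervals where appropriate, and then "p values from a binomial test to assess that responder rates are greater than zero". It gives no other null value or reference rate. The rule covers the endpoints that SAP 5 goes on to define as yes/no variables: healing at Months 24 and 30 in Week 8 healers and in Week 8 non-healers, sensitivity improvement in Week 8 improvers and in non-improvers, and the 15-letter gain from baseline and from Week 8. Healing is the efficacy part of the primary objective (SAP 1.1).

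Protocol 10.3 supplies the level and direction: "Unless otherwise specified, the significance level used for statistical testing (for descriptive purposes) will be 0.05 and two-sided tests will be used". Protocol 10.3.2 foresees inferential tests of the efficacy endpoints against baseline and/or Week 8, and calls them descriptive. SAP 2.9 calls all efficacy analyses exploratory. SAP 9 records no change from the protocol.

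Three places in the protocol bear on what happens without a lasting drug effect:

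- Protocol 3, just after describing withdrawal of topical drugs and use of artificial tears: "While some Stage 1 NK patients may heal, many cases progress to Stage 2 NK".
- Protocol 3.2, on the two approval trials: 33.3% complete healing in patients "treated with vehicle in the REPARO trial", and for the US trial "16.7 percent of patients treated with vehicle had complete corneal healing at week-8".
- Protocol 6.2: patients may receive standard of care in follow-up, which may include commercial OXERVATE.

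**The concern.** A test is useful when its null describes what would be seen if nothing of interest were going on. A responder rate of exactly zero does not describe that here. Patients can heal on other care, can be re-treated, and count as improved in sensitivity on any change above 0 cm.

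Zero is also the boundary of the parameter space, where an exact binomial test has no sampling variation. It therefore cannot separate one responder in 37 from 30 in 37: both give p = 0.

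What is at stake is how the responder tables read. With a 0.05 level stated in the protocol, a near-zero p-value beside a healing rate in a single-arm study can be taken as statistical support for long-term efficacy. The clearest case is the Week 8 non-healers. One later healer would be significant in the exact test, although DEFENDO treatment had not produced healing by Week 8 and later care was unrestricted.

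**Working it through.** **Inputs**

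- Null rate 0, alternative above 0 (SAP 5).
- Level 0.05 (protocol 10.3).
- Upper limit on n: "The DEFENDO Study enrolled a total of 37 patients" (SAP 7). The sizes of the Week 8 subsets are not given, so n = 5, 10, 20 and 37 are assumed as a range.
- Illustrative true rates: 16.7% and 33.3% (vehicle healing, protocol 3.2), and an assumed 5%.

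The plan states no power or critical value for these tests, so there is no figure of its own to reproduce.

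**Step 1: the exact p-value.** With X ~ Bin(n, 0), P(X ≥ x) = 0 for every x ≥ 1, and P(X ≥ 0) = 1. The critical value is one responder at any n.

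**Step 2: the chance of p < 0.05 when the true rate is π.** By step 1 this is P(X ≥ 1) = 1 − (1 − π)^n. For example, 1 − 0.833^20 = 0.974.

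| True rate | n = 5 | n = 10 | n = 20 | n = 37 |
|---|---|---|---|---|
| 5% (assumed) | 22.6% | 40.1% | 64.2% | 85.0% |
| 16.7% | 59.9% | 83.9% | 97.4% | 99.9% |
| 33.3% | 86.8% | 98.3% | >99.9% | >99.9% |

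The probability reaches 95% from n = 17 at 16.7% and from n = 8 at 33.3%.

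**Step 3: a different form of the test.** SAP 5 does not say which binomial test is meant. A score statistic has zero variance at a null of 0. A Wald statistic with the sample variance is z = sqrt(n·x/(n − x)). For 1 of 20 this is sqrt(20/19) = 1.03, not significant. At a critical value of 1.96 it needs 4 responders at n = 20 (x = 3 gives 1.88, x = 4 gives 2.24) and also 4 at n = 37 (x = 3 gives 1.81, x = 4 gives 2.12). The chance of passing is then:

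| True rate | n = 20 | n = 37 |
|---|---|---|
| 16.7% | 43.5% | 88.7% |
| 33.3% | 93.9% | >99.9% |

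**Step 4: what the p-value adds to the interval.** The Clopper-Pearson lower limit is above zero exactly when x ≥ 1. One of 20 gives 0.1% to 24.9%; one of 37 gives 0.07% to 14.2%; none of 37 gives 0% to 9.5%. The interval therefore already carries the yes/no answer in the exact p-value, and shows the imprecision as well.

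**Step 5: contrast with a non-zero null (illustration only).** At n = 37 and one-sided 0.025, a null of 16.7% would need 12 responders (actual level 0.014) and a null of 33.3% would need 19 (actual level 0.018), against one responder for a null of zero.

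**The case against.** The strongest defence is that SAP 5 claims only that a rate exceeds zero and does not claim a drug effect. The tests are labelled exploratory and descriptive, the protocol says no formal hypothesis test will be made, and there is no success criterion. The exact interval stands beside the p-value. Zero also has a recognisable origin. Week 8 non-healers and non-improvers have a Week 8 rate of zero by construction, and so does any gain measured from its own starting visit. It can thus be read as the comparison with baseline or Week 8 that protocol 10.3.2 asks for.

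The labels stand, and they limit the consequence. They do not make the number informative. The origin of the zero explains the choice but does not rescue it: a rate that is zero because of how the subset was selected is still not the later rate expected without drug effect. For Week 8 healers the reasoning does not apply at all.

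A reader might also infer more than the documents support:

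- *That untreated Stage 1 NK heals.* The protocol speaks of artificial tears and of vehicle, not of no treatment.
- *That a treatment without effect would almost always look significant.* At 16.7% the exact test passes only 60% of the time at n = 5, and the subset sizes are unknown.
- *That one responder always gives a tiny p-value.* This holds for the exact form and fails for the Wald form (step 3).
- *That the vehicle rates are the right null.* They are 8-week healing rates from trials in NK whose stage mix the protocol does not report. They are no benchmark for maintained healing, for sensitivity or for the 15-letter gain.

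**Conclusion.** The point holds in a limited form. In exact form, the planned responder p-value only reports whether the count is above zero, and it adds nothing to the planned Clopper-Pearson interval. That conclusion needs no outside rate and no assumed sample size.

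The probabilities in the table are illustrations. They rest on the vehicle rates as a stand-in for healing without a lasting OXERVATE effect, on assumed subset sizes up to 37, and on the exact form. A Wald form weakens them (44% at n = 20 and 89% at n = 37, for 16.7%) without making zero a meaningful null. For sensitivity and the 15-letter gain the documents give no background rate, so no probability can be tied to those endpoints.

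The harm is a misleading p-value in the responder tables, including those for the healing part of the primary objective. No formal decision, estimate or interval is wrong. The change should be made because it is nearly free, but the study does not depend on it.

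**What to change.** 1. In SAP 5, delete the clause that plans "p values from a binomial test to assess that responder rates are greater than zero", with its linking words. Report each responder rate as n/N with the Clopper-Pearson 95% interval.
2. Drop that p-value wherever the shells show it for Tables 14.2.1.1, 14.2.1.2, 14.2.2.2, 14.2.2.3, 14.2.5.2 and 14.2.5.3. The shells are a separate document and were not available, so this has to be checked there.
3. Add one sentence to SAP 5, for instance: *A responder rate above zero is not in itself evidence of a treatment effect, because NK can heal without OXERVATE and standard of care is allowed during follow-up.*
4. In SAP 9, replace the statement of no changes with an entry that responder endpoints carry no inferential test, as a departure from protocol 10.3.2.

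The cost is a few lines of SAP text and a check of six shells, with no new data or patients. The responder endpoints lose a p-value that carries no information, and SAP 9 gains one entry.

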6.2 PRIOR AND CONCOMITANT MEDICATIONS

Patient topical medications taken between exiting the DEFENDO Study and enrolling in the DEFENDO Long-Term Follow-up Study will be documented as prior medications.

Patients may be treated according to the standard of care as determined by the Investigator. This may include commercially available OXERVATE™ 0.002% (20 mcg/mL) cenegeamin-bbj ophthalmic solution. Any treatment history will be documented (including over-the-counter drugs, systemic medications, herbal products, vitamins, and antacids) on the Concomitant Medications electronic CRF (eCRF) page. Medication entries should be specific to product name (if a combination drug product) and spelled correctly. The dose, unit, frequency, route of administration, start date, discontinuation date, and indication should also be recorded. For medications administered only one time, the frequency column may reflect "once."

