9.3.2 Relationship of AEs to a Medicinal Product

The Investigator will assess the possible relationship between the AE and the investigational medication used in the DEFENDO Study and any treatment received, including Oxervate as standard of care, in this DEFENDO Long-Term Follow-up Study, according to the criteria in the below table.

Relationship of the Adverse Event to the Medicinal Product

Unrelated	No reasonable possibility that the administration of the Medicinal Product caused the event, no temporal relationship between the Medicinal Product and event onset, or an alternate etiology has been established.
Related	It is known to occur with the Medicinal Product, is a reasonable possibility that the Study Product caused the AE, or there is a temporal relationship between the Medicinal Product and event. Reasonable possibility means that there is evidence to suggest a causal relationship between the Medicinal Product and the AE.

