1.2 Study Design

This clinical study will be a multi-center, open label, long-term follow-up study of the patients who were enrolled in the NGF0120 Study who had Stage 1 NK who were treated with OXERVATE™ 0.002% (20 mcg/mL) cenegermin-bk bj ophthalmic solution. All patients enrolled in the NGF0120 Study who are meeting

inclusion and no exclusion criteria and/or are not lost to follow-up will be eligible for the NGF0122 Long-Term Follow-up Study.

The NGF0120 Study duration was for a total of 34 weeks: a screening period of 2 weeks, followed by enrollment in 8 weeks of OXERVATE™ treatment and an Off-Treatment Follow-Up of 6 months. After completing enrollment in the NGF0120 Study, patients will be invited to enter the NGF0122 Long-Term Follow-up Study (all standard of care are permitted). Two (2) additional long-term follow-up visits will occur at 24- and 30-months to evaluate long-term clinical outcomes. During the NGF0122 Study, the patients may be treated at the physician's discretion. Any concomitant treatment must be documented. If warranted for patient safety, the Investigator may elect to see the patient at an Unscheduled Visit(s) to evaluate the patient.

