1.3.2 Concomitant Medications

All medications from the completion of the NGF0120 study until the end of extended follow-up period will be clearly documented on the Concomitant Medications electronic Case Report Form (eCRF) page. Medication entries should be specific to product name (if a combination drug product) and spelled correctly (generic and brand name if available). The dose, unit, frequency, route of administration, start date, discontinuation date, and indication should also be recorded. For medications administered only one time, the frequency column may reflect "once".

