Appendix 2 Tables, Listing, and Figures**List of tables**

Table Number	Table Title	Analysis Population
14.1.1	Analysis Populations	
14.1.2	Subject Disposition	Full Analysis Set
14.1.3	Visit Participation	Full Analysis Set
14.1.4	Demographics	Full Analysis Set
14.1.5.1	Medical History	Full Analysis Set
14.1.5.2	Ocular History	Full Analysis Set
CCI		
14.1.6.3	Non-ocular Medications during Extended Follow-up	Full Analysis Set
14.2.1.1	Percentage of Patients who Achieved Epithelial Healing at Week 8 and Had Healed during Extended Follow-up	Full Analysis Set
14.2.1.2	Percentage of Patients who Did Not Achieve Epithelial Healing at Week 8 and Had Healing during Extended Follow-up	Full Analysis Set
14.2.2.1	Corneal Sensitivity Changes from Baseline and Week 8 during Extended Follow-up	Full Analysis Set
14.2.2.2	Percentage of Patients Who Improved in Corneal Sensitivity from Baseline to Week 8 and Still Had Improvement during Extended Follow-up	Full Analysis Set
14.2.2.3	Percentage of Patients Who Did Not Improve from Baseline in Corneal Sensitivity at Week 8 and Had Improvement during Extended Follow-up	Full Analysis Set
14.2.3	Schirmer I Change from Baseline and Week 8 during Extended Follow-up	Full Analysis Set
14.2.4	TFBUT Change from Baseline and Week 8 during Extended Follow-up	Full Analysis Set
14.2.5.1	BCDVA Change from Baseline and Week 8 during Extended Follow-up	Full Analysis Set
14.2.5.2	Percentage of Patients Achieved a 15- letter Gain from Baseline in BCDVA during Extended Follow-up	Full Analysis Set
14.2.5.3	Percentage of Patients Achieved a 15- letter Gain from Week 8 in BCDVA during Extended Follow-up	Full Analysis Set
14.2.6	IDEEL Change from Baseline and Week 8 during Extended Follow-up	Full Analysis Set
14.2.7	EQ-5D-5L Change from Baseline and Week 8 during Extended Follow-up	Full Analysis Set
CCI		
14.3.1.1	Summary of Adverse Events during Extended Follow-up	Full Analysis Set
14.3.1.2	Frequency of Adverse Events by System Organ Class and Preferred Term during Extended Follow-up	Full Analysis Set
14.3.1.3	Frequency of Adverse Events by System Organ Class and Preferred Term and by Maximum Severity during Extended Follow-up	Full Analysis Set
14.3.1.4	Frequency of Adverse Events by System Organ Class and Preferred Term and by Closest Relatedness during Extended Follow-up	Full Analysis Set

Table Number	Table Title	Analysis Population
14.3.1.5	Adverse Event - MedDRA Glossary	Full Analysis Set

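### Healing at Month 24 and 30 is counted whatever treatment followed Week 8, including permitted OXERVATE; label the rows and add one row for healing without re-treatment

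*SAP*

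**What the plan says.** SAP section 5 splits the healing endpoint by Week-8 status. For patients healed at Week 8, the Month 24 and Month 30 outcome "will be summarized as a binary goal attainment variable (Yes/No) based on the subset of patients who achieved corneal epithelial healing at Week 8"; the central reading center decides the status. A parallel rule covers patients not healed at Week 8. Both use observed cases, with exact 95% confidence intervals where appropriate. The corresponding tables are 14.2.1.1, "Percentage of Patients who Achieved Epithelial Healing at Week 8 and Had Healed during Extended Follow-up", and 14.2.1.2, "Percentage of Patients who Did Not Achieve Epithelial Healing at Week 8 and Had Healing during Extended Follow-up".

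Treatment after the parent study is open. SAP 1.2 notes that "all standard of care are permitted". Protocol 6.2 says of standard of care: "This may include commercially available OXERVATE". Protocol 9.3.2 has the investigator judge causality for "any treatment received, including Oxervate as standard of care, in this DEFENDO Long-Term Follow-up Study".

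Medication use is recorded. SAP 1.3.2 covers "All medications from the completion of the NGF0120 study until the end of extended follow-up period", and states: "The dose, unit, frequency, route of administration, start date, discontinuation date, and indication should also be recorded". The treated eye is not among those fields. Protocol 7.1.1 takes the history of topical ocular medication since the parent study from retrospective chart review, patient interview or both.

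**The concern.** To maintain healing is naturally read as durability of the 8-week course given in the parent study. The planned row measures something else: whether the cornea is healed at the visit under whatever care was given since. A patient who stayed healed untreated and a patient who relapsed, had a second course of the same drug and healed again count alike. In Table 14.2.1.2, a Week-8 non-healer who healed after a second course is credited in the same way as one who healed without it.

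Healing is the efficacy part of the primary objective. If re-treatment occurred, the planned rate overstates healing achieved without it, and the healing tables do not show by how much.

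**Working it through.** **Inputs**

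- Upper limit for any row: 37 patients, the parent-study enrolment (Protocol 10.1, SAP 7). The sample size is not power-based, so there is no planned rate or power figure to reproduce.
- Denominator n: patients in the Week-8 subset who are assessed at the visit (SAP 5, observed cases).
- Interval: exact Clopper-Pearson, 95% (SAP 5).
- Numbers healed at Week 8, healed at each visit and re-treated: not given. Every count below other than 37 is assumed.

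**Step 1: what each row counts.** Let x be the number healed at the visit, and r the number of those who had OXERVATE in the study eye after Week 8.

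- Planned row: x/n.
- Healed and not re-treated, same denominator: (x − r)/n.
- Gap: x/n − (x − r)/n = r/n.

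**Step 2: size per patient (r = 1).**

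- n = 37: 100/37 = 2.7 points, the smallest possible.
- n = 20: 100/20 = 5.0 points.
- n = 10: 100/10 = 10.0 points.

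**Step 3: illustration with n = 20 and x = 16 (assumed).**

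| r | Healed and not re-treated | Exact 95% CI |
|---|---|---|
| 0 (equals planned row) | 16/20 = 80.0% | 56.3 to 94.3 |
| 1 | 15/20 = 75.0% | 50.9 to 91.3 |
| 2 | 14/20 = 70.0% | 45.7 to 88.1 |
| 4 | 12/20 = 60.0% | 36.1 to 80.9 |

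**Step 4: the denominator must be fixed.** If re-treated patients are dropped instead, the rate is (x − r)/(n − r − u), where u is the number re-treated but not healed at the visit. Again with n = 20 and x = 16:

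- r = 4, u = 0: 12/16 = 75.0% (47.6 to 92.7), below the planned 80.0%.
- r = 1, u = 3: 15/16 = 93.8% (69.8 to 99.8), above it.

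Four patients are re-treated in both cases, yet the rate moves in opposite directions, because dropping them conditions on an event after Week 8. Keeping all assessed patients in the denominator avoids this, and the rate can then only equal the planned one or fall below it.

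**Step 5: the planned test does not help.** SAP 5 adds a binomial test that the rate exceeds zero. Under a true rate of 0, the probability of one or more healed patients is 0, so a single healed patient rejects. The test says nothing about how healing was sustained.

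**The case against.** The strongest reply is that nothing here is wrong. The follow-up is openly real-world, standard of care is permitted by design, all efficacy analyses are exploratory, and status regardless of later care is what such a design naturally yields. That stands, and it is why the planned rows should be kept.

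Second, the report will not be silent on re-treatment. SAP section 4 plans medication tables by generic name, split into ocular and non-ocular, over the extended follow-up, so recorded OXERVATE use in that period should be visible. Listings 16.2.5 and 16.2.6.1 allow a patient-by-patient check by hand. This partly stands: the tables could show that nobody was re-treated. They do not link use to healing or to the eye, however, and the listings leave that work to the reader.

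Third, text is blacked out in SAP section 4, at the end of section 5 and in the table list, so a re-treatment analysis could exist there. It cannot be ruled out. The healing rules themselves are readable, and the visible table list runs from 14.2.1.2 straight to 14.2.2.1, so no further healing table appears to be hidden at that point.

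Fourth, Table 14.2.1.2 describes a status and makes no claim of durability. True; there the matter is attribution, and the label serves the same purpose.

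Fifth, a row based on OXERVATE alone still counts a patient who healed again after another treatment or procedure. That is a real limit and must be stated with the row.

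**Conclusion.** The concern holds, as an inexpensive gain in interpretability and not as an error in the planned summary. The readable plan counts healing at Months 24 and 30 regardless of treatment after Week 8, does not say so, and gives no healing rate free of OXERVATE re-treatment. The overstatement relative to that rate is r/n: at least 2.7 points for each healed, re-treated patient. The total is unknown because the documents give neither the Week-8 healing count nor the number re-treated. If no healed patient was re-treated, the two rows coincide, and showing that would support the durability reading. The conclusion assumes that no redacted analysis already links re-treatment to healing.

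**What to change.** - **Label.** Keep the planned rows of Tables 14.2.1.1 and 14.2.1.2 and mark them as regardless of subsequent treatment.
- **Add one row per visit, with exact 95% CI.** Healed at the visit with no recorded OXERVATE re-treatment of the study eye since Week 8. Keep all assessed patients in the denominator and count re-treated patients as not meeting the row.
- **Other treatments or procedures.** Whether any also count as re-treatment is for the sponsor to define before database lock, only where the data are collected and without knowledge of the healing grades. SAP section 8 plans a descriptive interim once the last patient is enrolled, and enrolment takes place at the Month-24 visit. The definition is therefore best fixed before that interim; otherwise, state what had been seen.
- **Start of the window.** The medication page of this study begins at completion of the parent study. Take Week 8 to Week 32 from the integrated parent-study data (SAP 1.4), or state that the row starts at parent-study completion.
- **Treated eye.** Query it for recorded OXERVATE use, or show the row both ways.
- **Footnote.** Two visits cannot show continuous healing. Because treatment history is gathered retrospectively, missed re-treatment would leave the added row too high.
- **If the database is already locked.** Report the row as a labelled post-hoc analysis, which Protocol 10.3.5 allows.

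The cost is one label and one row per visit in two tables, plus a few treated-eye queries among at most 37 patients. No new visit or procedure is needed. The downside for the sponsor is that the added rate can never exceed the planned one.
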